Appendix 1. Handling of missing date and time fields

All dates and times used in the analysis are supposed to be complete. Nevertheless, in certain situations it will be difficult or impossible to have a complete date or time, e.g., lost to follow-up patients. SAP Table 3 contains a list of dates/times that will be completed in case of missing information.

General rules for completion of dates are the following:

1. Dates are split in 3 parts: year, month and day. Year is the top level, month is medium level and day is low level. If a part expected to contain a number is numeric but the value is outside a valid range, the complete date is handled as missing. For example, if date = 32-NOV-2012 the whole date is considered to be missing.
2. If a part expected to contain a number is not numeric, i.e., contains values such as, for example, ND, NA, 2? it is considered as missing.
3. If a part is missing, all other parts of a lower level are considered to be missing, e.g., '21-ND-2012' is considered as 'NK-NK-2012'.
4. Missing parts are changed into acceptable non-missing values depending on the type of date to be replaced.

In the following table, 'lower limit' and 'upper limit' refer to the minimum or maximum, respectively, of a possible date. For example, if the day is missing, the lowest limit is the first day of the given month and the upper limit is the last day of the given month. If the day and month are missing, the lower limit refers to the first day of the given year and the upper limit to the last day of the given year. The earliest and the latest of different dates refer to the first or last date, respectively, when ordered in sequence.

SAP Table. 2 Handling of missing data and time fields

Type of Date / Time	Date / Time is incomplete	Date / Time is missing
Date of birth	Day missing: 15 th of the month Day and month missing: 30 th of June	No replacement
AE resolution date	The upper limit	No approximation, the AE is considered as ongoing in the analysis.
AE onset date	If the end date of the AE is not before the start of study drug, and if the study drug start falls in the range of possible dates, it is the study drug start date. In all the other cases, it is the lower limit.	Earliest date between the AE end date and the start of study drug.
Hospitalization discharge date	The upper limit	No approximation, the hospitalization is considered as ongoing in the analysis.

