Hospitalization admission date	If the onset date of the AE leading to hospitalization falls in the range of possible dates, it is the onset date of the AE. In all the other cases, it is the lower limit.	The onset date of the AE leading to hospitalization

Previous/concomitant medication start date	
Lower limit except when:
 
Not tagged as ongoing at baseline
 
AND
 
Medication stop date not collected or with the upper limit after the study drug start
 
AND
 
the treatment start day falls in the range of possible dates.
 
In which case it is the study drug start day
	No replacement, the medication is considered to have started before the study
Previous/concomitant medication end date	
Upper limit except when:
 
Medication start is before study drug start or missing
 
AND
 
Upper limit is after the study drug start
 
AND
 
Not tagged as concomitant at baseline.
 
In which case it is 1 day before study drug start
	No replacement (considered ongoing)
End of treatment	
Use the earliest date between the:
 
 • upper limit • last contact date • date of death (if applicable) 	
Use the earliest date between the:
 
 • last contact date • date of death (if applicable)
Death date	Use the lower limit	No replacement

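### Incomplete death dates are set to the first of the month or year with no floor at the last date known alive, so a death can precede a recorded visit or the first dose

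*SAP*

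**What the plan says.** The table in SAP Appendix 1 gives one instruction for an incomplete death date: "Use the lower limit". No condition is attached. A wholly missing death date is not replaced.

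The text above the table explains the limit by calendar alone: "if the day is missing, the lowest limit is the first day of the given month", and "If the day and month are missing, the lower limit refers to the first day of the given year". General rule 3 adds: "If a part is missing, all other parts of a lower level are considered to be missing". A death recorded with a known day and year but no month therefore also goes to 1 January. General rule 4 says: "Missing parts are changed into acceptable non-missing values depending on the type of date to be replaced". It does not define which values are acceptable.

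Several other rows do refer to known events:
- AE onset: subject to a condition on the AE end date, "if the study drug start falls in the range of possible dates, it is the study drug start date".
- Hospital admission refers to the onset of the AE that led to it.
- Medication start and end dates refer to study drug start.
- End of treatment, when that date is incomplete or missing, begins "Use the earliest date between the" and lists last contact and date of death among the candidates.

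Not every row does so. AE resolution and hospital discharge use a bare upper limit, and date of birth uses fixed values.

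**The concern.** SAP section 5.2.2 measures OS from treatment start to death. It counts death as a PFS event when there is no documented progression, and as the end of DOR on the same condition. A death date moved to the start of its month or year can land before a visit at which the patient was seen alive, or before the first dose. The SAP does not say what the analyst should do with such a record, so the repair would be improvised after the data are seen.

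All the error runs one way, towards earlier death. There is also a conditional second effect. If a patient's end-of-treatment date is itself incomplete or missing, the end-of-treatment row can select the too-early death date, which shortens treatment duration and TTF.

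**Working it through.** The plan states no figure that depends on this rule, so there is nothing to reproduce. The check applies the rule to dates.

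**Worked example (assumed dates).** First dose 12 March 2018; week-24 visit 27 August 2018 (day 168); true death 30 August 2018 (day 171).

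| What is recorded | Imputed death | OS, days | Against known events |
|---|---|---|---|
| Month and year | 1 Aug 2018 | 142 | 168 − 142 = 26 days before the week-24 visit |
| Year only | 1 Jan 2018 | −70 | 70 days before first dose |
| Either, with a floor at the last visit | 27 Aug 2018 | 168 | 171 − 168 = 3 days before the true date |

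**How often, and how far.** Inputs from the documents:
- 24-month recruitment and follow-up of up to 78 weeks, i.e. 546 days (SAP, Final analysis).
- A visit every 6 weeks on treatment (SAP section 6.2: weeks 12, 24, … alternating with weeks 6, 18, …).
- A visit every 12 weeks in follow-up (Protocol section 3.2).

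Assumptions, not in the documents:
- First dose is equally likely on any of 730 days (calendar years 2017–2018).
- Death is equally likely on any of days 1–546.
- The last date known alive is the last scheduled visit, with first dose counted as day 0.

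All 730 × 546 = 398,580 combinations were enumerated, with:
- Imputed date = lower limit.
- Shift = true date − imputed date.
- Floored date = max(lower limit, last visit).

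Where a figure is a range, its ends reflect 6- or 12-week visits and whether a visit on the day of death counts as a date known alive.

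| Result per incomplete death date | Day missing | Day and month missing |
|---|---|---|
| Imputed before last visit, 6-week spacing | 33–35% | 94% |
| Imputed before last visit, 12-week spacing | 18–19% | 89% |
| Imputed before first dose | 2.5% | 33% |
| Mean early shift, rule as written | 14.7 days (max 30) | 182 days (max 364; 365 in a leap year) |
| Mean early shift with floor, 6-week spacing | 11.1–11.4 days | 20–21 days |
| Mean early shift with floor, 12-week spacing | 12.8–12.9 days | 37–38 days |

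**What the missing floor itself costs.** With the day missing, the floor recovers 14.7 − 12.9 = 1.8 to 14.7 − 11.1 = 3.6 days, or about 2–4 days. The rest of the shift comes from choosing a lower limit at all and would remain. With the month missing, the floor recovers 182 − 38 = 144 to 182 − 20 = 162 days.

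**Averaged over all deaths.** The share of deaths with an incomplete date is not given, so a range is assumed.
- Day missing in 5–10% of deaths: the rule as written moves the mean by 0.05 × 14.7 = 0.7 to 0.10 × 14.7 = 1.5 days.
- Month missing in 1–5% of deaths: 0.01 × 182 = 1.8 to 0.05 × 182 = 9.1 days. With the floor this is 0.01 × 20 = 0.2 to 0.05 × 38 = 1.9 days.

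**The case against.** The best defence is that Appendix 1 describes the limits as bounds on a possible date and asks for acceptable values, and that its calendar examples are only examples. A sensible programmer would not accept a death before a visit. This shows the likely intent, but it supplies no rule: neither term is defined, no floor is named, and the examples given are pure calendar limits.

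A second defence is that an early death date is conservative for survival in a single-arm trial, because no such error can flatter the drug. That is true of the direction. It does not justify a negative survival time.

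A third is rarity. Survival is recorded at every on-treatment visit and through follow-up, and Appendix 1 expects dates to be complete, so year-only deaths should be uncommon. This is reasonable, though neither document gives a rate. Protocol section 5.3 lets follow-up contacts be made by telephone, and Appendix 1 itself provides for incomplete dates.

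A reader might also infer four stronger things that the documents do not support:
- That the missing floor causes the whole 15-day or six-month shift. With the day missing it causes only about 2–4 days.
- That death is the only row not tied to a known event. AE resolution and hospital discharge are also bare limits.
- That TTF is always shortened through the end-of-treatment row. That row acts only when the end-of-treatment date is itself incomplete or missing, so two defective dates in one patient are needed.
- That the trial's main conclusion is at risk. Confirmed ORR (SAP section 5.2.1) and the decision rule (SAP section 7.10) use no death date, and PFS is untouched by death once progression is documented.

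**Conclusion.** The gap is real and modest. The death-date rule has no floor, and applied literally it can produce deaths before recorded visits and negative survival times. These sequences are a minority of day-missing cases (about 18–35% before the last visit) and nearly all month-missing cases (about 89–94%). The bias is always early, in OS and in PFS and DOR where death is the event. It is small when only the day is missing and large when the month is missing.

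The percentages and mean shifts rest on uniform first-dose and death dates and on visits kept to schedule. The existence of the impossible sequences does not depend on those assumptions; it needs only a first dose or visit later in the same month or year than the imputed date. The total effect depends on how many death dates are incomplete, which is unknown. SAP section 9 records that accrual closed after the interim analysis, so the survival medians may rest on few events, and one or two misplaced deaths could move them. The primary endpoint and the Simon decision rule are unaffected. The point should be corrected, but it does not threaten the trial's main result.

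**What to change.** In the death-date row of the table in SAP Appendix 1, replace the instruction for an incomplete date with: the later of the lower limit and the last date known alive, never before first dose, and kept within the recorded month or year.

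- Use the last date known alive itself, not the day after. With a last contact on 31 August and a death recorded as August, the day after would fall in September; it would also rule out death on the day of last contact.
- Define the last date known alive as the last date on which the patient was documented alive. A telephone call that reports the death should not count.
- If that date is later than the recorded month or year of death, the two records conflict and should be queried, not imputed.
- Use the bounded death date in the end-of-treatment row.
- List every imputed death date with the recorded parts and the date used.

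The cost is one table cell, a short definition and one listing. No sample size, decision rule or data collection changes, and the downside is negligible.

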Appendix 2 List of protocol deviations

Description	Category	Deviation excludes from analysis set?		
		Full Analysis / safety set	Per protocol set	Biomarker analysis set
Informed consent form not signed	Inclusion/Exclusion criteria	Yes	Yes	Yes
Outdated versions of informed consent signed	Inclusion/Exclusion criteria	Case by case	Case by case	Case by case
IMP no administered	Treatment	Yes	Yes	Yes
Without histological confirmation of locally advanced or metastatic, non-squamous non-small cell lung cancer (NSCLC).	Inclusion/Exclusion criteria	No	Yes	No
Without an activating EGFR mutation.	Inclusion/Exclusion criteria	No	Yes	Yes
Without concomitant T790M mutation.	Inclusion/Exclusion criteria	No	Yes	Yes
Patients without a M1a stage or M1b or locally advanced disease for which there is curative treatment	Inclusion/Exclusion criteria	No	No	No
ECOG>2	Inclusion/Exclusion criteria	No	No	No
No measurable or evaluable disease (as per RECIST 1.1 criteria). With the exception of pts with asymptomatic and stable brain metastases.	Inclusion/Exclusion criteria	No	Yes	No
Patients without having a pre-dose and a postdose valid result.	Biomarkers	No	No	Yes
Life expectancy <12 weeks.	Inclusion/Exclusion criteria	No	Case by case	No
Adequate organ function	Inclusion/Exclusion criteria	No	Case by case	No
Without capacity of swallow or complete the study.	Inclusion/Exclusion criteria	No	Case by case	No
No relevant toxicities at baseline	Inclusion/Exclusion criteria	No	Case by case	No
Patients who have received prior antineoplastic treatment for advanced disease.	Inclusion/Exclusion criteria	No	Case by case	No
Second active neoplasia	Inclusion/Exclusion criteria	No	Case by case	No

<6 months with prior treatment with cytotoxic chemotherapy for advanced NSCLC.	Inclusion/Exclusion criteria	No	Case by case	No
Patients who have received prior EGFR treatments for lung cancer.	Inclusion/Exclusion criteria	No	Case by case	No
Patients who have received treatment with an investigational drug within 3 weeks before the first day of study treatment.	Inclusion/Exclusion criteria	No	Case by case	No
Treatment with prohibited drugs within 14 days before the first day of study treatment.	Inclusion/Exclusion criteria	No	Case by case	No
Prohibited concomitant medication	Efficacy and safety	No	Case by case	No
Hypersensitivity to IMP	Investigational Medicinal Product	No	Case by case	No
Serious concomitant systemic disorder, including conditions that could interfere with absorption	Investigational Medicinal Product	No	Case by case	No
IMP overdose	Investigational Medicinal Product	No	Case by case	No
IMP underdose	Investigational Medicinal Product	No	Case by case	No
IMP administration dosing/schedule	Investigational Medicinal Product	No	Case by case	No
IMP toxicity	Investigational Medicinal Product	No	Case by case	No
Tumor assessment not done	Efficacy	No	Yes	No
Tumor assessment out of the window	Efficacy	No	Case by case	No
No baseline tumor assessment	Efficacy	No	Yes	No
No post-baseline tumor assessment	Efficacy	No	Yes	No
Subject not withdrawn as per protocol	Safety	No	Case by case	No

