2.2 Secondary objectives

- To determine the safety and tolerability profile of osimertinib (AZD9291), measured using the number and severity of AEs entered into the Case Report Form (CRF); chemistry, blood count, vital signs, physical examination, weight, ECG and performance status (ECOG).
- To determine secondary efficacy parameters such as the progression-free survival (PFS), overall survival (OS), time to treatment failure (TTF), duration of response (DOR), disease control rate (DCR) and tumor shrinkage (TS).
- To correlate the parameters of clinical response efficacy documented with the EGFR mutational status.
- To carry out a longitudinal analysis of EGFR mutations (including the T790M mutation) in plasma and serum.
- To determine levels of BIM mRNA as well as mRNA levels of other biomarkers related to EGFR TKI response and determine whether they are predictors of treatment response.
- To identify mechanisms of acquired resistance to osimertinib (AZD9291); mutations at the site of covalent binding to the drug (C797) or other mutations in tissue or blood.
- To analyze biomarkers related to mechanisms of resistance to the treatment.

Secondary efficacy endpoints: Patient safety and adverse events will be assessed using the Common Terminology Criteria for Adverse Events (CTCAE) of the U.S. National Cancer Institute (NCI), version 4. Grade 3 or 4 adverse events and serious adverse events will be assessed to determine the safety and tolerability of the various combinations of drugs.

Secondary efficacy endpoints:

- The progression-free survival (PFS) is defined as the time from the start of the treatment to death or disease progression, assessed by the investigator in accordance with RECIST v1.1, regardless of whether the patient has discontinued the study treatment or is receiving treatment with another drug.
- Overall survival (OS) is defined as the time from the start of treatment to the time of death due to any cause.
- Time to treatment failure (TTF) is defined as the time from the start of treatment to the time at
 which the patient discontinues treatment due to any cause, including disease progression
 assessed by the investigator in accordance with RECIST v1.1, toxicity, death or at the
 patient's request.
- Duration of response (DOR) is defined as the time from the first documented response to documented disease progression or death, in accordance with RECIST 1.1 criteria.

Protocol date: May 21, 2018 Version 3

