Biological sampling: Given that very little is known on how cancer develops resistance to pyrimidine-based EGFR inhibitors, mutations in tumor tissue or blood will be identified at the site of covalent binding to osimertinib (AZD9291) (C797) in addition to other mutations that can mediate resistance.

The first tissue samples should be taken before starting study treatment (see Appendix 6 for more details on tissue sampling procedures). Tumor re-biopsy will be considered at the time of progression (as recommendation only) for analysis of possible mechanisms of resistance and future translational research at the reference laboratory.

The first blood samples for serum and collection of plasma should be taken before starting study treatment (see Appendix 6 for more details on blood sampling procedures). The following samples should be taken at 2 weeks, and every 12 weeks thereafter (coinciding with assessments of responses using radiographic imaging) and at the time of progression.

At the time of site activation, the sponsor will provide cryovials and cryoboxes for the storage and transport of samples, as well as labels. This material will be provided by the central laboratory. No other cryovials or labels should be used for this study. If more tubes and labels are required, these should be requested from the sponsor in writing at least 3 weeks before they are required (see Appendix 6).

Anamnesis and demographic data: Anamnesis includes clinically significant diseases, surgical interventions, history of cancer (including prior antineoplastic treatments and procedures), history of smoking, alcoholism, drug addiction, as well as any medications (e.g., prescribed drugs, overthe-counter drugs, medicinal plants, homeopathic remedies, or food supplements) used by the patient in the 21 days prior to screening visit. Demographic data will include age, gender and race/ethnicity reported by the patient himself/herself.

Vital signs: These will include the measurement of height (only during screening), weight, respiratory rate, heart rate, blood pressure, and body temperature. Abnormal or significant changes in vital signs from baseline should be recorded as adverse events, if appropriate.

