8.4 Populations for analysis

Full population for efficacy and safety analysis

It includes all patients who have received the investigational treatment, regardless of the degree of compliance with the protocol.

Per-protocol population (PP):

Per-protocol population includes all patients of the full population for analysis that have not presented any protocol violations that may affect the assessment of the primary endpoint of the study (major protocol violations).

Population for biomarker analysis

All patients included in the full population for analysis whose biomarkers have been assessed.

Efficacy analyses are performed on the full population for analysis and the per-protocol population. The full analysis set population will be the primary population for the efficacy analyses.

The biomarker analysis will be performed on the population for biomarkers. The

safety analysis will be performed for the full analysis population.

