7.4 Analysis populations

(ICH E3; 9.7.1, 11.4.2.5. ICH E9; 5.2)

Full Analysis and Safety analysis set (FAS)

Includes all included subjects who have received any study drug, independently of the degree of adherence to the protocol.

Per Protocol Set (PP)

The Per Protocol set includes all patients included in the FAS who did not violate the protocol in a way that might affect the evaluation of the effect of the study drug on the primary endpoint, i.e., without a major protocol violation.

Major and minor protocol violations will be identified by clinically trained personnel before the database lock. The definition of the major protocol violations is described in **Appendix 2**.

Biomarker analysis set

All patients included in FAS who has been evaluable for biomarker status.

Sensitivity analysis

Primary efficacy analysis will be performed on the full analysis (FAS) and PP sets. Secondary efficacy analysis will be performed on FAS. FAS will be considered the primary population for the efficacy analysis.

Biomarker analysis will be performed on biomarker analysis set.

Safety analysis will be performed on the full analysis set.

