7.5 Covariates and subgroups

(ICH E3; 9.7.1, 11.4.2.1. ICH E9; 5.7. CPMP 2002; 4.CPMP 2003.)

Difference between baseline tumor measurements and those observed throughout the study will be analyzed using the Wilcoxon test. Patients with and without different types of EGFR mutation will be compared. For binary outcomes (cORR, ORR and DCR), the chi-square or Fisher's exact test will be used. For time objectives (PFS, OS, TTF and DOR), the Kaplan-Meier method and log-rank test will be used. For continuous objectives (percentage of Tumor Shrinkage, TS), the Mann-Whitney U test will be used.

Baseline biomarker levels will be correlated with the clinical response. For binary and continuous results, the Spearman correlation will be used. For time objectives (PFS), the Kaplan-Meier method and log-rank test will be used. The categorization or log-transformation of biomarker levels will be considered.

The feasibility of re-biopsies at the time of progression will be estimated with the number and percentage of patients with rebiopsy and 95% confidence interval.

The presence of mutations and biomarker levels (tissue or blood) will be compared from baseline to time of progression with the Mc Nemar and Wilcoxon tests, respectively.

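### SAP Appendix 2 requires a post-dose result for the only biomarker set, although the baseline-predictor analyses need none and SAP 7.4 and Protocol 8.4 set no such condition

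*SAP*

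**What the plan says.** The biomarker population is described in three places.

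- Protocol 8.4: "All patients included in the full population for analysis whose biomarkers have been assessed".
- SAP 7.4: "All patients included in FAS who has been evaluable for biomarker status".
- SAP Appendix 2: the row "Patients without having a pre-dose and a postdose valid result" is marked as no exclusion for the full analysis and per-protocol sets, and as an exclusion for the biomarker set. Other rows allow case-by-case decisions; this one does not.

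There is one such set, and SAP 7.4 applies it throughout: "Biomarker analysis will be performed on biomarker analysis set".

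SAP 7.5 puts two kinds of analysis on it. In the first, "Baseline biomarker levels will be correlated with the clinical response", using Spearman correlation, and Kaplan-Meier with log-rank for PFS. This serves the Protocol 2.2 objective of measuring BIM and other mRNA levels to "determine whether they are predictors of treatment response". In the second, "The presence of mutations and biomarker levels (tissue or blood) will be compared from baseline to time of progression", using McNemar and Wilcoxon tests.

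Post-dose samples come from two sources. Blood is scheduled at week 2, every 12 weeks, and at progression (Protocol 5.2; SAP Table 1 in 6.2). Tissue depends on a re-biopsy. Protocol 5.2 says "Tumor re-biopsy will be considered at the time of progression (as recommendation only", and Protocol 5.3 makes the same non-binding suggestion after progression or discontinuation for any reason. SAP Table 1 lists tissue at the end-of-treatment visit if it can be had. Protocol 3.2 and SAP 6.1 instead state that a biopsy is to be done when the treatment phase ends.

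**The concern.** Whether a baseline marker predicts response or PFS can be analysed in every treated patient with a valid baseline value. Requiring a later sample as well makes entry depend on what happens after treatment starts. If the chance of having that sample is related to response or progression, the analysis selects on the outcome it is meant to predict.

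The requirement suits the paired comparisons, which cannot be done without both values. Nothing in the SAP confines it to them. Two analysts, one working from SAP 7.4 and one from Appendix 2, could build different sets from the same data, and the choice could be made after results are known.

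**Working it through.** **1. What each analysis needs**

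| Analysis (SAP 7.5) | Pre-dose value | Post-dose value |
|---|---|---|
| Baseline level against response or PFS | needed | not needed |
| Baseline against progression (McNemar, Wilcoxon) | needed | needed |
| Appendix 2 row, as applied to the whole set | required | required |

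The row fits the second analysis and over-restricts the first. It adds a condition that is absent from SAP 7.4 and Protocol 8.4.

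**2. Denominator.** The documents give no size for the biomarker set and no re-biopsy rate. The only stated figure is the planned 73 patients. That design reproduces: summing b(21, x, p) × P(Bin(52, p) ≥ 45 − x) over x = 12 to 21 gives 0.0249 at p = 0.50 and 0.9004 at p = 0.70, matching the stated 0.025 and 90%. SAP Section 9 reports that accrual closed after the interim analysis, and the final number is not given. I therefore also show 21, the stage 1 size, as an assumed lower case.

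**3. Any post-dose blood result qualifies.** With 95% of patients having a valid post-dose sample (assumed), 73 × 0.95 ≈ 69 remain, or 21 × 0.95 ≈ 20. Little is lost.

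**4. The post-dose result must be in tissue, obtained at progression.** Retained = N × share progressing × share re-biopsied, with 40-80% and 30-70% assumed.

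- N = 73: 73 × 0.40 × 0.30 = 8.8, up to 73 × 0.80 × 0.70 = 40.9.
- N = 21: 21 × 0.40 × 0.30 = 2.5, up to 21 × 0.80 × 0.70 = 11.8.

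For orientation, with exponential PFS the share progressing by 78 weeks (18 months) is 1 − exp(−ln 2 × 18 / median). This is 71% for a median of 10 months and 39% for 25 months (medians assumed).

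**5. Tissue required, but taken at end of treatment for any reason with equal uptake.** At 30-70% uptake, 73 × 0.30 = 22 to 73 × 0.70 = 51 remain. If every patient reaches that point and uptake is unrelated to the reason for stopping, numbers are lost but PFS is not selected on.

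**6. Direction of the bias under step 4.** Take two marker groups with median PFS of 10 and 25 months (assumed), a ratio of 25 / 10 = 2.5. Keep only those who progress by 18 months. With S = exp(−ln 2 × 18 / median), the median among them is −ln(1 − (1 − S)/2) × median / ln 2. This gives 6.36 and 7.89 months, a ratio of 7.89 / 6.36 = 1.24. Re-biopsy uptake does not enter this calculation, so better uptake alone would not remove the attenuation.

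The response mix shifts too. With ORR 70%, and 50% of responders and 90% of non-responders progressing (assumed), ORR among progressors is 0.35 / (0.35 + 0.27) = 56.5%.

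**7. Precision.** The Spearman correlation detectable with 80% power at two-sided 0.05 is approximately tanh[(1.960 + 0.842) / √((n − 3)/1.06)].

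| n | 73 | 40 | 21 | 20 | 10 |
|---|---|---|---|---|---|
| detectable correlation | 0.33 | 0.44 | 0.59 | 0.60 | 0.80 |

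**The case against.** The best defence is that the row was probably written with the scheduled blood draws in mind. It sits in a list of protocol deviations, and a patient still responding who has not had a merely recommended re-biopsy has not deviated from anything. SAP 7.5 speaks of levels in tissue or blood, and a valid week-2 sample could satisfy the row. On that reading nearly everyone stays. This stands, and it is why no single loss figure can be given.

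A reader might infer the stronger point that the set consists mainly of progressors who had an optional re-biopsy, and that most of the sample is lost. The documents do not support that as a general statement. The row names neither marker nor specimen. BIM mRNA is listed without a specimen in Protocol 2.2 and SAP 5.2.3. Tissue may also come from patients who stop treatment for reasons other than progression, and the documents disagree on whether that biopsy is expected or only suggested.

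It could also be argued that Appendix 2 simply spells out what SAP 7.4 means by evaluable. But SAP 7.4 points to that appendix for major protocol violations, not for biomarker evaluability, and Protocol 8.4 asks only that biomarkers were assessed. Even if the argument is accepted, the baseline analyses still carry a requirement they do not need.

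**Conclusion.** The point holds as a conflict in the definition of the set and an unnecessary condition on the baseline-predictor analyses. That part rests on the text alone.

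The consequence is conditional. It is small if any post-dose blood result qualifies. If tissue is required and comes only from re-biopsied progressors, about 9 to 41 of 73 remain (about 2.5 to 12 if only 21 were enrolled), and the marker-PFS association is attenuated. Those figures rest on assumed progression and re-biopsy shares, and the attenuation example on assumed exponential PFS. They are not predictions for this trial. If only about 21 patients were enrolled, precision is poor even with nobody excluded, so a power loss worked out for 73 patients would not describe it.

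The reach is limited. The SAP classes the biomarker endpoints as exploratory (the protocol lists them as molecular secondary endpoints), and both documents call all efficacy analyses exploratory. The row leaves the full analysis and per-protocol sets unchanged, so the primary ORR analysis is unaffected. It should still be settled before the biomarker data are analysed.

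**What to change.** Replace the single biomarker set in SAP 7.4 with two:

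1. **Baseline biomarker set:** FAS patients with a valid pre-dose result for the marker and specimen being analysed. Use it for all baseline-predictor analyses.
2. **Paired biomarker set:** FAS patients with valid pre-dose and post-dose results for the same marker in the same specimen type. Use it only for the baseline-to-progression McNemar and Wilcoxon comparisons.

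Restrict the Appendix 2 row to the paired set and align SAP 7.4 with it. For each marker, report the number excluded from each set, with reasons. The differing statements on the end-of-treatment biopsy should also be reconciled, because they determine who can enter a tissue-based paired set.

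The cost is SAP wording and one extra population flag in the programming. No new data are needed.
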